The objective of the proposed research is to evaluate a promising strategy for CPAP level selection: a physiologic approach minimizing V/Q mismatch and measured non-invasively at the infants bedside. We propose the following specific Aims and hypotheses in support of this objective: Aim 1 (primary): measure the responsiveness of V/Q mismatch to a strategy of individualized CPAP level selection. We hypothesize that V/Q mismatch will, on average, improve by 10% of baseline V/Q mismatch at the best identified CPAP level. Aim 2: describe the distribution of best CPAP levels as identified by our strategy. Best CPAP levels will be described as both absolute values and relative to baseline (+2 cm H₂O, -1 cm H₂O, etc.). For this exploratory aim, we hypothesize that a best CPAP will be identified above the baseline in greater than 50% but less than 80% of subjects. Demonstrating that most but not all infants benefit from higher pressures will highlight the importance of individualized CPAP level selection in premature infants.

Primary outcome variable(s)

Primary outcome measure: V/Q mismatch. This parameter will be calculated by computer software on the basis of the curvilinear characteristics generated by a best-fit curve connecting the FiO₂/SpO₂ pairs obtained during the study protocol. With lower V/Q and greater mismatch, the curve is progressively displaced to the right relative to a curve corresponding to an ideal reference lung (interrupted, left-most curve in Figure 2, see attached documents). The V/Q ratio is displayed on the software output after the FiO₂/SpO₂ pairs are input. Additionally, this parameter is also displayed as the degree of right-shift relative to the ideal reference lung (greater values indicate more mismatch), providing a positive continuous number with units of % FiO₂ as an alternative measure to the ratio value with greater ease of use. This will be measured twice at baseline without a change in CPAP level and then following each CPAP level change. The primary outcome measure is the responsiveness of V/Q mismatch to a strategy of individualized CPAP level selection, measured as the improvement in V/Q mismatch between the second baseline level and best identified CPAP level for each subject (see Figure 3 in attached documents.) For infants not responding to either +1 or -1 cm H₂O CPAP level changes, baseline CPAP will be defined as best, with zero assigned as the improvement in V/Q mismatch.

Secondary outcome variable(s)

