
No active consideration of endotracheal intubation; as determined by the clinical Attending of record. 2. No hemodynamic instability, defined as a baseline heart rate less than 100 beats per minute (bpm) or greater than 180 bpm; or a mean arterial blood pressure of less than 30 millimeters of mercury (mm Hg). 3. No supplemental FiO₂ requirement greater than 0.45. 4. No capillary/arterial partial pressure of carbon dioxide greater than 65 mm Hg on last blood gas analysis, unless performed more than 6 hours prior. 5. No more than 6 apnea/bradycardia/desaturation events requiring tactile stimulation or more than 1 requiring positive pressure bag ventilation in the preceding 6 hours. Initiation of the study protocol will be deferred until these criteria are met. Figure 3 depicts the study protocol as applied in one hypothetical subject. Of note, the protocol will vary between subjects with respect to the direction and extent of CPAP level changes, as determined by the absence or presence of a response at each step-wise CPAP level change. This is described in detail below. Subjects will undergo the study interventions in their routine clinical environment. The clinically selected CPAP interface and pressure source will be maintained. A study pulse-oximeter, with low motion artifact and a short averaging time, will be placed on a post-ductal limb and used for SpO₂ measurements. V/Q will first be measured on two separate occasions 30 minutes apart at baseline CPAP, set by the clinical team. The repeat baseline measures will allow an estimate of the stability of V/Q as a function of time (further discussed in Confounding under Analysis Plan). To measure V/Q mismatch, gradual changes in delivered FiO₂, followed by SpO₂ measurement, will be applied to obtain three FiO₂/SpO₂ pairs, one each for SpO₂ values in the ranges of 85-87%, 89-91% and 93-95%. To obtain each SpO₂ range, FiO₂ will be titrated gradually until SpO₂ falls within the desired values. After 60 seconds of stabilization at the identified FiO₂ value, SpO₂ will be recorded every 30 seconds for 2 minutes if an adequate signal waveform is present, providing up to four SpO₂ values. These values will be averaged to calculate the SpO₂ value used for the FiO₂/SpO₂ pair, acknowledging the inherent instability of pulse-oximeter values over time in premature infants. A computer software program will immediately calculate V/Q from the identified FiO₂/SpO₂ pairs at the bedside. Next, CPAP will be increased by +1 cm H₂O. A period of 15 minutes will elapse to allow equilibration of lung volumes in response to the CPAP level change (24). V/Q calculations as described above will be repeated. A positive response will be defined as an improvement in V/Q at the new pressure level of 5% relative to the preceding CPAP level. Responders will undergo subsequent stepwise +1 cm H₂O increases up to +3 cm H₂O from baseline or 8 cm H₂O; whichever is less. Infants not responding to the initial +1 cm H₂O increase will return to baseline CPAP for 15 minutes and then be assessed at -1 cm H₂O from baseline. Infants responding at this lower CPAP level will undergo an additional decrease to -2 cm H₂O from baseline or 3 cm H₂O; whichever is greater. The allowed range of -2 to +3 cm H₂O reflects our institutional practice of typically setting a baseline CPAP level of 5 or 6 cm H₂O and a CPAP pressure range of 4 to 8 cm H₂O used in international trials. Best CPAP will be defined as the lowest (and last) CPAP level at which a positive response, as defined above, is measured. The baseline CPAP level will be defined as best for those infants not responding to either +1 or -1 cm H₂O CPAP level changes, with a corresponding V/Q improvement of zero. Upon completion of the study protocol, infants will be returned to their baseline CPAP level. The study protocol will typically require between 60 and 120 minutes. Throughout the study, a set of pre-defined stopping criteria will be monitored to ensure subject tolerance of the study procedures. These criteria are designed to be conservative safety measures and will result in study termination and provision of supportive care, as needed. Patient Safety Considerations: Extensive patient safety considerations minimizing the risks associated with implementation of this phase II design research protocol have been incorporated: 1. Many of the key eligibility (inclusions and exclusion) criteria reflect the deliberate selection of a premature infant population that is inherently less vulnerable and at lower risk of common morbidities of prematurity and less likely to suffer any adverse outcomes from implementation of the study procedures. a) I1. Corrected gestational age 27-35 weeks (GA): this selects a study population in which respiratory distress syndrome is common and CPAP is frequently used, while avoiding less mature infants with a CGA less than 27 weeks who are more prone to physiologic instability. We exclude this population in consideration of safety for this phase II study despite a high risk of CPAP failure and a potential for benefit from our long-term research goals of establishing methods to prevent CPAP failure. b) I2. Chronologic age of greater than 24 hours. This avoids study of infants during the first 24 hours of life when they may be more prone to physiologic instability. c) I3. On continuous CPAP support for greater than 24 hours. This prioritizes safety by restricting study to subjects demonstrating stability on CPAP therapy, in contrast to infants newly transitioned to CPAP without a period of demonstrated tolerance. d) I4. Supplemental oxygen requirement, with a fraction of inspired oxygen (FiO₂) 0.25 for at least 2 consecutive hours. This ensures that CPAP level changes are only performed in infants requiring supplemental oxygenation, suggesting V/Q mismatch and/or shunt from atelectasis. These subjects would plausibly benefit from carefully monitored changes in continuous distending airway pressure to counteract the pathophysiology resulting in the oxygen need. This criteria avoids CPAP

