
The following documents are currently attached to this item:

There are no documents attached for this item.

Deception

Does your project use deception?

No

International Research

Are you conducting research outside of the United States?

No

Analysis Plan

Results will be summarized using basic descriptive statistics. For Aim 1, a paired t-test for parametric results or a Wilcoxon signed-rank test for non-parametric results will be used to test our hypothesis that V/Q mismatch will improve at best CPAP level compared to baseline. For Aim 2, we will calculate the proportion of subjects in which best CPAP level is identified above the baseline pressure level to assess our hypothesis that this occurs in greater than 50% but less than 80% of subjects. Further, best CPAP for the cohort will be summarized as mean and standard deviation (if parametric) or median and interquartile range (if non-parametric). No formal statistical testing of significance will be performed for this second descriptive Aim. The change in V/Q over the two baseline periods, as well as the change in heart rate and blood pressure between baseline and best CPAP levels will be tested using the statistical approach as Aim 1. We predict the null hypothesis of no significant difference for these comparisons. Should a significant change in V/Q be identified between baseline periods, we will perform an additional analysis comparing the change in V/Q between baseline periods to the change in V/Q between baseline and best CPAP level to account for the independent impact of time on V/Q

mismatch. Confounding: key elements of our study design limit confounding for Aim 1, to measure the responsiveness of V/Q mismatch to a strategy of individualized CPAP level selection. The use of a pre-post within-patient analysis limits confounding from variation in between-patient characteristics. A remaining important source of confounding is the possibility that V/Q simply improves over time irrespective of CPAP pressure changes. We account for this by measuring V/Q on two separate occasions 30 minutes apart at baseline CPAP in the study protocol, facilitating an assessment of the stability of V/Q over time.

The following documents are currently attached to this item:

There are no documents attached for this item.

Data confidentiality

- Paper-based records will be kept in a secure location and only be accessible to personnel involved in the study.**

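### The comparison meant to account for change in V/Q over time depends on a significant baseline test in 20 infants, and no scaling for elapsed time is stated

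*Combined protocol and SAP*

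**What the plan says.** The Analysis Plan states the risk itself: "A remaining important source of confounding is the possibility that V/Q simply improves over time irrespective of CPAP pressure changes". Its answer is the repeated baseline: "We account for this by measuring V/Q on two separate occasions 30 minutes apart at baseline CPAP in the study protocol". The change between the two baselines is always tested by the Aim 1 method (paired t-test or Wilcoxon signed-rank). The expected result is stated too: "We predict the null hypothesis of no significant difference for these comparisons". The step that compares the baseline change with the baseline-to-best change is conditional: "Should a significant change in V/Q be identified between baseline periods, we will perform an additional analysis". No formula is given for that comparison.

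Under Primary outcome variable(s), the primary contrast is "measured as the improvement in V/Q mismatch between the second baseline level and best identified CPAP level for each subject". The same section says of V/Q mismatch: "This will be measured twice at baseline without a change in CPAP level and then following each CPAP level change". Infants who respond in neither direction are assigned zero.

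Under Procedures, the 15-minute wait is written for the first upward step: "A period of 15 minutes will elapse to allow equilibration of lung volumes in response to the CPAP level change". An infant who does not respond at +1 goes back to baseline CPAP for 15 minutes before being assessed at -1. Response is judged against the previous level: "A positive response will be defined as an improvement in V/Q at the new pressure level of 5% relative to the preceding CPAP level". The whole procedure is said typically to take 60 to 120 minutes.

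**The concern.** The trial has one arm, so no control group separates the effect of CPAP from the passage of time. The repeated baseline is the only source of information on drift. Under the plan, that information enters a formal comparison only if a small test is significant, and the authors predict that it will not be. A non-significant result in 20 infants is compatible with no drift and also with a drift large enough to matter. If the comparison is skipped, the report gives a primary improvement with no time-accounted figure beside it.

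There is a second gap when the comparison is made. The baseline change covers 30 minutes. The baseline-to-best change covers an interval that depends on the path each infant takes. Setting one against the other without regard to time does not isolate CPAP.

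At stake is how Aim 1 is read: how much of an observed improvement (10% is hypothesised) could be time.

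**Working it through.** **1. The plan's own figure.** Accrual gives n = 20, a 10% change, an SD of the difference of 15% and two-sided alpha of 0.05. Paired t-test power uses the noncentral t with 19 df and noncentrality (10/15) × √20 = 2.98. The result is 80.7%, against 80% stated (n = 19 gives 78.5%). The figure reproduces, but it applies to a 10% change.

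**2. The same test as the condition for the comparison.** Noncentrality is (drift/d) × √20, where d is the SD of the baseline-to-baseline difference. The 95% CI half-width is 2.093 × d/√20. Drift and d are assumptions; 15% is borrowed from the plan's SD for the primary difference.

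| d (%) | significant, drift 2% | drift 3% | drift 5% | CI half-width (points) |
|---|---|---|---|---|
| 5 | 40% | 72% | 99% | 2.3 |
| 7.5 | 21% | 40% | 81% | 3.5 |
| 10 | 14% | 25% | 57% | 4.7 |
| 15 | 9% | 14% | 29% | 7.0 |

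**3. Elapsed time.** One V/Q reading takes at least 3 × (1 + 2) = 9 minutes, before FiO₂ titration. Minutes run from the end of the second baseline reading to the end of the best-CPAP reading.

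| Best level | explicit waits only | 15 min at every step |
|---|---|---|
| +1 | 15 + 9 = 24 | 24 |
| +2 | 33 | 48 |
| +3 | 42 | 72 |
| -1 | 24 + 15 + 9 = 48 | 63 |
| -2 | 57 | 87 |

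A reading at the returned baseline would add 9 minutes on the downward path (57 and 66, or 72 and 96). The two rules quoted above on readings after each change and on the preceding level support such a reading, but Procedures does not list it. So the range is 24 to 66 minutes on explicit waits, and up to 87 or 96 with a wait at every step.

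Check against the stated total: the second baseline ends at about 30 + 9 = 39 minutes. The -2 path then totals 39 + 87 = 126 or 39 + 96 = 135 minutes, above the typical 60 to 120. On explicit waits it totals 96 or 105, which fits.

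**4. Size of the drift contribution.** This is a simulation of 400,000 infants with no CPAP effect, linear improvement of 3% per 30 minutes, and independent reading error with SD d/√2. The 5% rule is applied against the preceding level and non-responders are set to zero. Points added to the mean improvement at d = 5, 7.5, 10 and 15%:

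| Timing | with re-read | without |
|---|---|---|
| 15 min at every step | 3.2, 3.5, 3.6, 3.7 | 4.3, 3.9, 3.7, 3.5 |
| explicit waits only | 2.1, 2.5, 2.6, 2.8 | 3.0, 2.8, 2.7, 2.6 |

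With no drift at all, the mean improvement is already about 1.6 to 8.2 points, from selecting levels on noisy readings.

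**5. If drift settles.** Suppose 3% over the baseline interval, then exponential decay. With a 30-minute half-life the next 30 minutes bring 3 × 1/2 = 1.5%; with a 15-minute half-life, 3 × 1/4 = 0.75%. Linear scaling would still subtract 3%. In the simulation (15 minutes at every step) it subtracts about 1.3 to 2.2 times the true drift part at a 30-minute half-life and 2.4 to 4.8 times at 15 minutes.

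**6. Precision of an adjusted estimate.** Let k = mean interval/30. Because the second baseline is shared, the SE ratio is √((225 + k²d² + kd²)/225). In the simulation the cohort mean interval, with zero-assigned infants included, is about 16 to 33 minutes, so k = 1 is a fair guide. It gives 1.11, 1.22, 1.37 and 1.73 at d = 5, 7.5, 10 and 15%. At d = 15% the effective SD is 15 × 1.73 = 26.0, and power for a 10% effect falls from 81% to 37%. With no drift, the gap between the two estimates has SD d/√20: 2.24 points at d = 10 and 3.35 at d = 15. It exceeds 5 points by chance 2.5% and 14% of the time.

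**The case against.** Much of the plan points the right way. The baseline change is always tested and results are to be summarised descriptively, so drift is always examined; only the change-against-change comparison is conditional. Starting the primary contrast at the second baseline excludes earlier drift. Infants must have been on CPAP for more than 24 hours, and the procedure is deferred until stability criteria are met, which should limit drift. All of this stands and bounds the point. It does not remove it, because the plan still calls time an important confounder after describing its within-infant design.

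The comparison has no formula, so scaling is unspecified rather than excluded. That stands: the finding is that no scaling is stated.

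The size is assumed, and only improving drift was simulated. That also stands. If d is 5% or less, the test detects a 3% drift fairly well, and mainly the missing scaling remains.

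A time-adjusted estimate is no cure. It is imprecise where the test is weak, it over-subtracts if drift settles, and it leaves selection bias untouched. At d of 10% or more that bias (4.5 to 8.2 points with no drift) exceeds the drift part. This is why the adjustment belongs in a labelled sensitivity analysis and not in place of the primary test.

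**Conclusion.** The point holds in a limited form. The plan makes its only time-accounting comparison depend on a test that, for an assumed 3% drift per 30 minutes, is significant between 72% (d = 5%) and 14% (d = 15%) of the time. It states no scaling, although intervals differ by path. Under linear improving drift and no CPAP effect, about 2 to 4 points of mean improvement would be credited to CPAP. That figure rests on assumed drift, linearity and d.

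Three stronger readings are tempting and not supported:
- **That the plan ignores drift, or that a reader could learn nothing about it.** The baseline change is always tested.
- **That 2 to 4 points of drift are to be expected.** The documents give no drift, direction or repeat-reading SD.
- **That intervals of 87 to 96 minutes are what the protocol prescribes.** The 15-minute wait is written only for the first upward step and the return to baseline, and those paths overrun the typical total.

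**What to change.** In the Analysis Plan:

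1. Delete the significance condition. Always report the baseline-to-baseline change with its 95% CI, and always report its comparison with the baseline-to-best change, whatever the p-value.
2. Keep the primary test as it is.
3. Add a labelled sensitivity analysis: the baseline-to-best improvement after subtracting the cohort mean drift, in two versions. One carries the drift forward unscaled. The other scales it linearly to each infant's recorded minutes from second baseline to the best-CPAP reading. Leave zero-assigned infants at zero, and bootstrap infants for the CI so that uncertainty in the drift is carried through.
4. State that linear scaling over-subtracts if drift settles, that neither version removes bias from selecting the best level, and that a gap between the estimates can arise by chance.

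The cost is analysis wording and a time stamp on each reading; no CPAP step or measurement procedure changes. The adjusted estimate is less precise: an SE 1.1 to 1.7 times the unadjusted one at a 30-minute mean interval, so it may be inconclusive at high SD. More true responders would lengthen the mean interval. At 48 minutes (k = 1.6) the same formula gives 1.2 to 2.3 times, and a chance gap above 5 points occurs 16% of the time at d = 10 and 35% at d = 15.

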This study will enroll up to 30 patients in order to evaluate 20 subjects. Infants will be screened for eligibility by the research team using routinely available clinical data from the electronic health record. Informed consent will be obtained from parents or guardians approached within the HUP ICN, PAH ICN, or the CHOP N/IICU during the eligibility window as described below. The diagram depicted in Figure 4 summarizes expected enrollment in consideration of our eligibility criteria and additional barriers to successful recruitment and study application. This estimate suggests a 10-month window of active enrollment will be required to meet our recruitment goals, making our one-year recruitment goal feasible. Aim 1 guides sample size considerations. Using a paired test of correlated means, a sample size of 20 evaluated infants will provide 80% power to detect an overall average percent change of 10% from baseline, assuming a 15% standard deviation of the difference and a two-sided alpha level of 0.05.

Key inclusion criteria

I1. 27-35 weeks corrected gestational age (CGA) by best obstetric estimate, determined by the clinical obstetric team during antepartum admission and chronologic age, measured from date of birth I2. Chronologic age greater than 24 hours, measured from time of birth. I3. On CPAP support between 4-8 cm H₂O for greater than 24 hours, as document on the bedside infant flow sheet. I4. Supplemental oxygen requirement, with a fraction of inspired oxygen (FiO₂) 0.25 for at least 2 consecutive hours, as documented on the bedside infant flow sheet. (Infants without an oxygenation requirement are unlikely to have significant V/Q mismatch. Further, FiO₂ titrations (see Procedures) are required to apply the non-invasive technique, resulting in limited applicability to infants with little or no supplemental oxygen requirement).

Key exclusion criteria

E1. Congenital anomalies, as determined by the clinical supervising physician. E2. Current or prior air leak syndrome, as determined by the clinical supervising physician.

Vulnerable Populations

Children Form

Pregnant women (if the study procedures may affect the condition of the pregnant woman or fetus) Form

Fetuses and/or Neonates Form

Prisoners Form

Other

None of the above populations are included in the research study

The following documents are currently attached to this item:

There are no documents attached for this item.

Populations vulnerable to undue influence or coercion

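### If V/Q mismatch significantly worsens between the two baselines, the planned time analysis favours CPAP almost by construction, because non-responders enter it with an assigned zero

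*Combined protocol and SAP*

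**What the plan says.** Objectives, Primary outcome variable(s), defines the Aim 1 outcome as responsiveness "measured as the improvement in V/Q mismatch between the second baseline level and best identified CPAP level for each subject". For infants who respond to neither +1 nor -1 cm H2O, "baseline CPAP will be defined as best, with zero assigned as the improvement in V/Q mismatch". The Procedures section repeats the rule: baseline counts as best, "with a corresponding V/Q improvement of zero". A response is a 5% improvement on the preceding CPAP level.

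Procedures also calls for two V/Q measurements 30 minutes apart at the baseline CPAP level, so the change between baselines is observed in every infant.

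The Analysis Plan tests that change with the Aim 1 methods (paired t-test or Wilcoxon signed-rank) and expects no difference. If it is significant, an additional analysis follows, "comparing the change in V/Q between baseline periods to the change in V/Q between baseline and best CPAP level to account for" the independent effect of time. The trigger has no direction, although the accompanying text on confounding mentions only improvement over time. The test for the additional analysis is not named, and nothing suspends the zero rule for it.

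**The concern.** To separate CPAP from time, both changes must contain whatever time does. The change between baselines does. An assigned zero does not: it is the value given to an infant whose later readings were set aside, whatever those readings were. Responders enter with a measured improvement of at least 5%. The second change therefore cannot be negative, while the first can.

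Suppose the cohort drifts worse during the session and CPAP has no effect. Most infants fail both +1 and -1 and score zero. The comparison then asks whether zero is better than a negative trend, which the trigger has just established. It does not ask whether CPAP did better than time. This is the only analysis planned for what the Analysis Plan calls a remaining important source of confounding, so a significant result from it could be taken as support for the strategy.

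**Working it through.** **The plan's own figure.** Accrual plans for a mean change of 10% of baseline, takes 15% as the SD of the within-infant difference with two-sided alpha 0.05, and concludes that "a sample size of 20 evaluated infants will provide 80% power". With d = 10/15 = 0.667, the noncentral-t power of a paired t-test is 80.7% at n = 20 and 78.5% at n = 19. The figure of 20 is reproduced and is not at issue.

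**The limiting case, by algebra.** For each infant let D1 = baseline 1 - baseline 2 (negative means worsening) and D2 = baseline 2 - best CPAP. If all 20 infants are non-responders, D2 = 0 for all. The paired comparison then uses D2 - D1 = -D1, and t(D2 - D1) = -t(D1). This is the trigger test with its sign reversed and the same p-value. Whenever the trigger fires for worsening, the comparison is significant in favour of CPAP. The Wilcoxon version behaves identically.

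**The general case, by simulation.** Inputs from the documents: n = 20, baselines 30 minutes apart, 15 minutes of equilibration per step, the 5% response rule, steps of +1 to +3 then -1 and -2, and zero for non-responders. Each V/Q measurement needs three SpO2 ranges at 1 + 2 = 3 minutes each, so the +1 reading falls about 15 + 9 = 24 minutes after baseline 2, excluding titration time. No fresh reading on return to baseline is described, so -1 was judged against baseline 2.

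Inputs assumed, because the documents give none:
- Worsening of 2-5% of baseline per 30 minutes.
- Between-infant drift SD of 0 or 3%.
- Single-reading SD of 1-10.6%. The upper end is 15%/√2 = 10.6%, the value if the whole planning SD were reading error.

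The CPAP effect was set to zero. The additional analysis was taken as a two-sided paired t-test of D2 - D1 at 0.05, run only after a significant worsening, with 20,000 trials per scenario.

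Results:
- **Given the trigger**, the comparison favoured CPAP in about 99-100% of trials in every scenario; the nominal rate in that direction is 2.5%. Separate runs with Wilcoxon and unpaired Welch tests, with worsening up to 10% per 30 minutes, gave 100%.
- **Example A** (3% worsening, drift SD 3%, reading SD 2%). The SD of D1 is √(3² + 2×2²) = √17 = 4.12%, so the expected t is about -3/(4.12/√20) = -3.25. The trigger fired in 87% of trials. The primary test was significant in 1.6% of those and the comparison favoured CPAP in 100%.
- **Example B** (5% worsening, no drift variation, reading SD 5%, steps about 25 minutes apart). Non-responders were 91% of infants; mean D2 was +0.8% against mean D1 of -5.0%. The trigger fired in 85% and CPAP was favoured in 99.8% of those.
- **How often the analysis is run** varies widely. With 2% worsening and no drift variation, trigger plus false credit occurred in 40% of all trials at reading SD 3.5%, 22% at 5%, 14% at 7% and 8% at 10.6%. With larger drift and small reading error it approached 100%.
- **High reading error.** At reading SD 7-10.6% and 2-3% worsening, only 55-72% of infants scored zero. The other 28-45% were false responders, and the primary test was itself significant in 73-98% of all trials. There, selection of the best level contributes as well as the zero rule.

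**With the zero replaced.** The test of (baseline 2 - first +1 reading) - (24/30)×D1, with no assigned value, favoured CPAP in about 2.5% of trials when always run. Run only after a significant worsening, it favoured CPAP in up to about 25% at reading SD 10.6%, because baseline 2 enters both changes and the trigger selects on it.

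**The case against.** The case on the other side has four parts.

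First, a reader might infer that the analysis credits CPAP nearly every time V/Q worsens. The documents do not support that. The 99-100% applies only once the baseline change is significant, and with small drift or noisy readings that may be rare. This stands, and the point is stated conditionally.

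Second, the plan's stated worry is improvement, and it predicts no baseline change. Infants must have been on CPAP for more than 24 hours and pass stability checks, and stopping criteria apply. The documents give no evidence that cohort-wide worsening is likely. This stands as to likelihood. It does not remove the defect, since the trigger as written covers worsening.

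Third, at high reading error much of the false credit comes from choosing the best level on noisy readings, a separate problem that also affects the primary test. This stands for that range. At low reading error and uniform drift, every infant scores zero, the primary test is never significant, and the comparison still favours CPAP every time.

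Fourth, a reader might infer that the result would be reported as a CPAP effect independent of time, or would override a null Aim 1 result. Nothing in the Analysis Plan says so; it is called an additional analysis. Equally, nothing makes it depend on the Aim 1 result or says how it is to be read.

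**Conclusion.** The concern holds in conditional form. The time analysis compares a measured change with one that is zero or positive by rule, so after a significant worsening between baselines it cannot account for time: it favours CPAP in about 99-100% of the trials in which it is run, even when CPAP does nothing. That result is exact when all infants are non-responders. Elsewhere it rests on the assumed drift and reading error, and it did not change across the values or tests tried. The frequency with which the analysis would be run does depend on those assumptions, at about 8-100% of trials for 2-5% worsening per 30 minutes and reading SD 1-10.6%. The sample size and the definition of the Aim 1 outcome are not called into question by this point. The change should be made, because the analysis cannot do its stated job in a case that its own trigger admits.

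**What to change.** Replace the additional analysis in the Analysis Plan with text to this effect: in every infant, and regardless of whether the baseline change is significant, the measured change from baseline 1 to baseline 2 will be compared with the measured change from baseline 2 to the first +1 cm H2O reading, each divided by its actual elapsed time; the paired difference will be reported with a 95% CI; assigned zeros will not be used.

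Dropping the trigger is part of the fix, given the inflation that remains when the replacement is run only after a significant baseline change. Keep the assigned zero for the Aim 1 outcome only, and say that it is not used to judge the effect of time.

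The cost is a sentence or two. Both baselines and the first +1 reading are already taken, before any branching; elapsed times must be recorded, because the 24 minutes omits titration. The limits should be stated: this supportive analysis covers the first +1 step and not the full strategy, so an infant helped only at a lower level counts against CPAP; it assumes roughly linear drift; and it will favour CPAP less often than the present comparison.
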